We will be recruiting through a non-VA research team that works between two local sites - the Brigham and Women’s Pain Management Center and the Martinos Center for Biomedical Imaging at Massachusetts General Hospital. Their active study, titled the COMFORT study, is presently recruiting participants for fibromyalgia, and will often receive chronic pain patients who do not have fibromyalgia but may be eligible for our study. We will provide them with recruitment materials (currently approved pamphlets) to provide to patients who are ineligible for their study so that we may be able to boost our recruitment. The study staff with COMFORT will not be screening participants for us, and will only be providing patients who fail screening for the COMFORT study with our information as an alternative study to participate in. No sensitive information that has been collected by the COMFORT staff will be shared with our facility. We will use our approved phone screen to screen such participants as they call into our study. In addition, we will be providing patients at our facility who fail screening the opportunity and information to participate in the COMFORT study in

the same way. We will provide them with contact information for the COMFORT study via a flier the COMFORT study has provided our team. We will not be screening participants for the COMFORT study and any sensitive information we may have collected from participants during our screening session will not be shared with the COMFORT study staff.

With respect to the recruitment of women, my mentor [name] is a research affiliate of the Women's Health Science Division, National Center for PTSD, which is directed by [name], who is also a consultant on this project. Thus, Drs. [name] and [name] will be instrumental in the recruitment of women into the study from that venue. Patients responding to advertisements or otherwise referred will be directed/asked to telephone the PI or a psychology technician to be scheduled for an in-person screening evaluation. Within the past decade, there is an increasing trend of women Veterans receiving care in the VA due to the significantly increased number of women serving in the current OEF/OIF/OND conflicts.⁶⁸ Also, VABHS is a unique site given the co-location of many women Veteran services, such as women's primary care, the Women's Health Sciences Division of the National Center for PTSD, and one of the few Women's Stress Disorder Treatment Teams (WSDTT) in the country. These services draw women Veterans from all over the country. Currently, 3,238 women Veterans are using care at VA Boston, of which we serve 3100 in women's primary care and 276 in the WSDTT. Nevertheless, we anticipate some difficulty reaching our projected recruitment of 50% women Veterans. Therefore, we will also target women in the community (Veterans and non-Veterans) and our research technician will post advertisements in local areas such as community mental health centers, coffee shops, laundromats, local newspapers and college campuses, as well as online sites such as Craigslist. We have already successfully implemented these strategies for our other research studies including women and are confident that we will be able to recruit the required number of women for the proposed study (n = 30) in order to conduct gender comparisons.

Screening Evaluation for Study Eligibility: If considered potentially eligible and interested, participants will be invited for an in-person screening session in which they will first complete the informed consent process, according to the guidelines established by the Institutional Review Board (IRB) at the VABHS. After providing informed consent, the subject will answer assessment questionnaires and receive a physical examination, laboratory blood tests, a urinalysis, a urine toxicology test for illicit drugs, and an EKG. In addition to the initial qualitative "yes/no" test for tobacco use, we will test participants' urine cotinine level using Nymox NicAlert semi-quantitative test strips. Cotinine is the principal metabolite of nicotine and has a longer half-life (18 hrs vs. 2 hrs), and thus can be reliably used to estimate daily intake of nicotine. Cotinine tests will detect any tobacco use for the past few days, and therefore will be sensitive enough to test for any recent tobacco use when participants present for exercise assessment sessions. Although we will not be excluding tobacco users from the study, any level of tobacco use can impact accurate measurement of the antistress and antinociceptive neurohormones under investigation, therefore it is imperative that we are able to capture the level of cotinine for the participants who smoke and verify the non-smoking status of participants who identify as non-smokers. Finally, women will receive a urine pregnancy test at all in person study visits. The physical screening will be performed by [name] or her medical fellows.

**** Parts of the physical examination, lab tests, or the EKG and psychiatric assessments may be repeated in order to clarify results, or to track or evaluate possible medical/psychiatric problems during the study. To do this, the participant may be asked to return for an extra visit for which he/she will be compensated.**

****If a month or more of time lapses between the screening session and the baseline cold pressor assessment sessions, we will repeat the CAPS-5 to re-determine PTSD status, prior to any study procedures with the exception of the urine testing. Regardless of the outcome of the assessment, the participant will be compensated for the full amount of the cold pressor session.**

Potential chronic pain participants will participate in a one-time meeting with an MD or Co-I, who specializes in rehabilitative medicine, for confirmation of an ICD-10 chronic pain diagnosis and to receive medical clearance to exercise. The screening evaluation will also include a semi-structured interview from which important demographic and descriptive information will be obtained. The assessment will include the Structured Clinical Interview for DSM-5 (SCID) and the Clinician Administered PTSD Scale (CAPS-5). 1. These assessments will be administered in order to confirm a diagnosis of PTSD by the PI or other PhD-level trained staff. The CAPS-5 specifically will be done either in-person or over the phone in a private room during their appointment at VA Boston. CAPS-5 assessments over the phone will only be conducted when the PI, or other approved PhD level staff, is present at VA Boston. If over the phone, the CAPS-5 data will be input directly into our secure data drive via VPN access with a VA-issued laptop, therefore there will be no hardcopy data kept remotely. In the event of an emergency during the CAPS-5 telephone assessment, [name] and her team will be on the floor during the assessment and [name], as the PI, will intervene to ensure safety as indicated in the human subjects section, part B, below. The assessor over the phone will be in direct contact with [name] via email or text and can indicate an emergency without patient identifiers. VA TBI screen will be administered to identify those potentially suffering from comorbid TBI. These assessments will be audiotaped for purposes of diagnostic consensus and will follow IRB guidelines for storage and disposal based on the VA retention schedule. The PI or other PhD-level trained staff will be administering these assessments for which she has received formal approval. Self-report measures of pain, PTSD and exercise motivation also will be administered. Patients meeting inclusion criteria will be offered participation in the remainder of the study. All patients who decline the study or do not meet study criteria will be given feedback on the evaluation results and offered an alternative treatment (e.g., pain management and/or PTSD treatment offered through the VABHS). Individuals who are not Veterans will be given a referral list of chronic pain and PTSD providers in the surrounding area. The entire screening evaluation will take approximately 3-4 hours to complete. A timeline for the administration of the assessment instruments is provided below, after the next section.

**** The laboratory blood tests will include a complete blood count, other red blood cell or iron indices if indicated, B12 or possibly folate levels, electrolytes, glucose measure(s), liver function tests, a hepatitis screen if indicated, cholesterol or other lipids if indicated, thyroid function tests, or other tests that may be needed to evaluate a specific medical problem you might have. Women may receive a follicular stimulating hormone (FSH) level test to determine if they are perimenopausal.**

****Additional blood tests will be administered during the baseline cold pressor, mid-point and endpoint assessment sessions. These tests will measure vitamin D3, sedimentation rate CBC, C-reactive protein, and a lipid profile in order to explore the potential association of changes among these labs over time with potential improvements in chronic pain symptomatology over time.**

Overview of Experimental Testing Procedures:

****Please note that if an unforeseen circumstance arises such that the in-person scheduled assessment session needs to be cancelled, this session can be reschedule. For women participants, the session would need to be rescheduled during her follicular phase such that it could take up to an additional 28 days for the rescheduled session.**

Scheduling for Women: For each MAX-EX test, female participants will be scheduled between 2 and 7 days after the start of menstruation during the early follicular phase of the menstrual cycle when both progesterone and estrogen levels are at their lowest and comparable to levels in male participants. For women who are perimenopausal/menopausal, they will be scheduled during the same timeline as the male participants.

For participants on any medication that could put them at additional cardiac risk during the MAX-EX test (baseline and endpoint), an additional EKG will be done on the morning prior to MAX-EX testing and will be reviewed by the covering cardiologist immediately. Should the EKG indicate that CPX testing will put the participant at any additional cardiac risk, the participant will be withdrawn from the study; however he or she still will be paid in full for the session.

Cardiopulmonary Exercise Test (CPX): All participants will complete a MAX-EX test within one to five days of the cold pressor test session (see below under Cold Pressor Test Session). During each test, we will be using rigorous means to control for the many confounders that potentially impact baseline NPY and ALLO levels as well as the pattern of neurotransmitters, peptides, and steroids released in response to exercise. Once eligibility is confirmed, the participant will present as scheduled, for the exercise testing session at the Clinical Studies Unit (CSU) and the entire session will take place between 8am and 12pm. In addition to our stringent, inclusion/exclusion criteria, participants will have been instructed to abstain from food and beverages, except for water, after midnight the evening before and to abstain from breakfast at home on the day of the testing procedure. Upon arrival at VABHS, the subject will be given water and power bars (6 kcal/kg) to provide the same baseline caloric load for all participants. The “breakfast” will be provided two hours before exercise, so that feeding-induced increases in ACTH, cortisol, glucose and other reactants will have returned to baseline before the first baseline blood sample is taken. During this time, they will also be completing self-report questionnaires (see Table 2). The MAX-EX testing will be performed in accordance with guidelines published by the American College of Cardiology.⁶⁹ Participants will sit in a comfortable chair for 60 minutes prior to testing. A catheter will be placed in a large superficial vein of the left arm. Once ready for exercise testing, the participant will be transported to the exercise testing room via wheelchair. The participant will then be shifted onto the upright testing bicycle and electrocardiogram electrodes will be applied at least 15 minutes prior to testing. During the MAX-EX, oxygen consumption (peak VO_2) and ventilatory anaerobic threshold (VAT),

will be measured in order to assess fitness capacity and correlate with blood lactate, ALLO and NPY levels sampled at each increase in exercise load. Participants will exercise using a standard bike protocol with 2 minute stages. After an unloaded warm-up stage, all subjects will complete the first stage with 50W of resistance. Based on the subject's size and baseline fitness level, the stages will increase in increments of 20, 25, or 30 W at the discretion of our experienced exercise physiologist. Adjustments to incremental increases may also be made by the exercise physiologist to allow subjects to reach their maximum exercise capacity within comparable ~15 minute time frames. Confirmation that the subject reached VO_2 peak will be based on meeting 2 of 3 criteria: 1) respiratory exchange ratio >1.1 ; 2) plateau of the VO_2 with increased load; 3) achievement of age-targeted heart rate; 4) the patient is no longer able to continue or it is medically unsafe for them to continue. If at any time, participants wish to terminate or are unable to perform the exercise assessment, we will terminate the session after an appropriate and safe cool-down period. During the MAX-EX test itself, plasma will be drawn at the end of each stage, so that changes in plasma levels of the neuromodulators of interest can be linked in real time to changes in the oxidative status of the participant (anaerobic versus aerobic). Blood sampling will be performed at two points prior to exercise (-15 minutes and -0 minutes), during the last 30 sec of each exercise workload, and at 5 and 30 minutes post exercise testing for measurement of the steroids and neuropeptides of interest.

All MAX_EX assessment visits and training sessions will be conducted by a team of ACLS credentialed staff (cardiologist, nurses, and exercise physiologist). A defibrillator and code cart are maintained in the immediate vicinity. Consistently, CR and CSU staff participate in regular mock emergency codes to maintain expertise with emergency management. Furthermore, visits will only be completed during the time that the Urgent Care Center is open and when the hospital code team is available for emergency responses.

Cold Pressor Test (CPT): Measures of pain sensitivity will be obtained using the CPT, a procedure that has been used widely in laboratory studies to measure pain perception and tolerance,⁷⁰ as well as self-report measures of pain severity and disability and exercise motivation (Appendix 1). The cold pressor protocol will follow guidelines from a previously published study investigating similar variables.⁷⁰ Chronic pain mentor [name], who has experience administering the cold pressor test, will provide supervision. Participants will be instructed to hold their right hand in temperature-controlled ice water, inside a cold pressor apparatus, up to their wrist and to keep the hand still. They will be instructed to say when they first experience pain and will be told to withdraw their hand when the pain becomes intolerable. Therefore two measures of pain sensitivity will be derived: "pain threshold" and "pain tolerance". Pain threshold is defined as the number of seconds between hand immersion in the ice water and the first report of "pain." Pain tolerance is defined as the number of seconds between hand immersion and hand withdrawal from the water. A maximum seven-minute time limit for immersion, unknown to the patient, will be imposed. The CPT will be obtained: A) in relation to the acute maximum load exercise assessment (pre- and post-CPX), and B) in relation to progressive exercise training (before, at mid-point, and after completion).

A) Participants will perform baseline pain ratings and the CPT in the late morning **one to five days before** each CPX, two and a half hours after IV placement and the breakfast of power bars provided. Blood will be sampled from the IV for ALLO+PA measurement just prior to the pain ratings and CPT. Participants will have fasted since midnight, as per procedures for the CPX. The post-CPX pain ratings and CPT will be performed on the day of the CPX, immediately after the 30' post-CPX blood drawing for ALLO+PA. Obtaining the baseline and post-CPX pain assessments at the same time of day on two separate days will control for potential effects of diurnal variation on pain sensitivity, as well as ALLO+PA levels.

B) The procedures in A will be completed before and after completion of the chronic exercise training program.

C) In addition, the baseline pain ratings and CPT procedures in A will be performed at the mid-point of the progressive exercise training program.

D) After the first CPT visit, research study staff will program, explain and show the participant how to attach the activity monitor (known as an Actigraph) to record the participant's physical activity during exercise training sessions throughout the progressive exercise training phase of the study. Participants will be asked to wear the monitor only during exercise training sessions (three times per week) to evaluate change in physical activity over time.

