PROTOCOL: Neurobiological and Psychological Benefits of Exercise in

Chronic Pain & PTSD

NCT#- 03283163

(1). Rationale:

(a). Statement of the Problem.

The wars in Iraq and Afghanistan are creating a new generation of Veterans, including an increasing number of women Veterans, who present with comorbid PTSD and chronic pain conditions from recent deployment-related physical injuries and exposure to psychological trauma. Health behavior change has become increasingly important in treating these conditions and proactively preventing long-term negative health sequelae, in order to benefit these Veterans directly and reduce the growing challenges to our healthcare system. The proposed CDA-2 program of research will use an innovative translational research approach to study whether a chronic progressive -based exercise program will reduce chronic pain in patients with PTSD and to elucidate and modify potential PTSD-related deficiencies in neurobiological and psychological responses to exercise to optimize the physical and psychological benefits of exercise for these individuals.

(b). Hypotheses or Key Questions.

The overall aims and hypotheses of the current protocol are:

Aim 1: Assess the degree of clinical change in chronic pain and PTSD symptoms between the screening session, baseline and endpoint assessment time-points across a 12-week progressive exercise training program.

Hypothesis 1: As compared to the screening evaluation and baseline exercise assessment, as a result of the progressive exercise training regimen, participants will experience clinically significant reductions in pain related symptoms as well as improvements in symptoms of PTSD by the endpoint exercise assessment (between week 13-15).

Aim 2: Compare the impact of the exercise training program on plasma levels of the anti-stress neuromodulator, allopregnanolone plus pregnanolone (ALLO +PA), among trauma-exposed participants with comorbid chronic pain and vary degree of PTSD symptom severity (CP/PTSD).

Hypothesis2a: At the baseline exercise assessment, ALLO +PA will be lower and increase less in response to the maximum load exercise than during the endpoint exercise assessment (week 13).

Aim 3: Determine whether maximum load exercise-induced increases in plasma ALLO+PA correlate with changes in pain symptoms as measured by the cold pressor test and self-reported pain ratings.

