Summary: There has been a call for research for clinical trials of exercise with high risk populations,⁷ such as individuals suffering from chronic pain and PTSD. Therefore, because of the known psychological benefits of exercise on overall mental and physical health, and compelling recent research suggesting that exercise may address the biopsychosocial pathophysiology shared between chronic pain and PTSD (and other commonly comorbid conditions such as depression), we have designed a progressive exercise training program for this population. Our main objective is to determine whether chronic exercise can help reduce clinical symptoms of chronic pain and PTSD, including comorbid symptoms of depression. Secondly, we will investigate whether chronic exercise also impacts ALLO+PA, as well as nociceptive responses to exercise. We hypothesize that individuals with trauma exposure, chronic musculoskeletal pain and varying degrees of PTSD severity will INITIALLY be unable to experience the “anti-nociceptive and anti-stress” benefits of exercise due to deficits in the release of the antinociceptive molecules ALLO +PA. This may also contribute to amotivation for vigorous exercise and difficulty achieving long-term exercise maintenance, which is our second exploratory objective. We hypothesize that engagement in an enforced laboratory-supported chronic, intense exercise program will progressively enhance the capacity of such patients to synthesize and release ALLO+PA during exercise. This will be associated with a central perception of “reward”, reductions in pain sensitivity, reductions in PTSD symptoms, and overall improvements in mood and vigor. These biopsychological benefits may then increase the intrinsic motivation and self-efficacy for exercise and promote the long-term adoption

of exercise outside of the laboratory. Over time, this may help to reduce disability from PTSD severity and chronic pain and improve the overall quality of these participants' lives.

(b). Significance.

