To explore the relationship between exercise VO_2 max and the neurobiological factors of interest in relationship to pain variables, bivariate correlations were conducted. Significant correlations with respect to VO_2 max were found for change in ALLO ($r=.77$, $p<.01$) and for NPY at the anaerobic threshold ($r=.61$, $p<.05$), as well as for change in NPY from baseline to 5' post-exercise ($r=.81$, $p<.01$). Also, a significant relationship was found between the pain threshold after exercise and a) change in ALLO, as well as b) change in NPY ($r=.61$, $p<.05$, and $r=.81$, $p<.01$, respectively). Finally the change in NPY and pain tolerance was significantly correlated ($r=.64$, $p<.05$).

Due to the observed significant correlations between pain threshold and change in ALLO, as well as change in NPY, these variables were entered into a multiple regression equation to predict pain threshold post exercise. It was found to be significant $F(2,9) = 13.38$, $p<.01$. In addition, for the change in NPY variable, the unstandardized partial slope (18.2) and standardized partial slope (1.2) were significantly different from 0 ($t=4.27$, $df=9$, $p<.01$); with every increase in pain threshold, NPY also increased.

[figure not shown]
Taken together, these preliminary data 1) trend in the right direction in support of our hypothesis

that NPY and ALLO levels are lower in the Pain/PTSD group as compared to the TC's, particularly for the men, though not significant at this point. 2) Importantly, we found that the changes in ALLO and NPY in response to maximum load exercise challenge were correlated with VO_2 max, suggesting that regular exercise leading to an increase in VO_2 max may result in an increase in the capacity for release of both of these antinociceptive molecules—with resultant reductions in pain. This latter assertion is supported by 3) our preliminary data showing that both change in NPY and change in ALLO in response to acute maximum load exercise correlated with pain tolerance and threshold in individuals with and without chronic pain and PTSD.

Prior work in PTSD

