Aim 1 : Hypothesis one will be evaluated by conditional LGMs. The Intercept of the LGM will be centered on the self report data from the baseline CPX assessment (i.e., first Slope loading will be fixed to 0.0). The intermittent time point (midpoint self-report session) will be freely estimated and the final time point (i.e the self-report data from the 13 week MAX-EX test session) will have a corresponding Slope factor loading fixed to 1.0. Accordingly, the mean and variance of the Slope factor will convey the fixed (average) and random effects (individual differences) of change for the time interval of interest. The two study groups will be dummy coded (using chronic pain/PTSD as the reference condition in the initial models) and included as predictors in the LGM to account for individual differences in symptom reduction (i.e. pain intensity, pain tolerance and threshold, depression and PTSD symptoms) due to treatment assignment. The Intercept will be regressed onto the treatment covariates to examine any pre-exercise training differences among treatment conditions. Moreover, individual differences in pre-treatment functioning will be held constant by regressing the Slope onto the Intercept. Hypotheses 1 will be supported in part by the statistical significance of the study group (dummy code) > Slope paths. In fact, these paths reflect study group x Time interaction effects. The nature of these interaction effects in the LGMs will be characterized using the procedures described by Curran, Bauer, and Willoughby.⁷⁸ All outcome measures will be analyzed in this fashion.

Aims 2 & 3: At both exercise assessment time-points, change scores will be computed ALLO+PA and these will be correlated with pain tolerance and pain threshold scores using Pearson or Spearman correlations, as appropriate. For exploratory purposes, ALLO+PA will be used as predictor variables in a regression equation to predict pain outcome (tolerance, threshold and intensity).

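### Aim 2 asks about ALLO+PA across PTSD severity, but its hypothesis and analysis contain no severity term, so a baseline-to-endpoint rise cannot show a PTSD-related deficit or its correction

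*Combined protocol and SAP*

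**What the plan says.** The Statement of the Problem sets out to "elucidate and modify potential PTSD-related deficiencies in neurobiological and psychological responses to exercise". Aim 2, under Hypotheses or Key Questions, compares the effect of training on plasma ALLO+PA "among trauma-exposed participants with comorbid chronic pain and vary degree of PTSD symptom severity (CP/PTSD"). Hypothesis 2a, the only hypothesis under that aim, predicts that at the baseline test "ALLO +PA will be lower and increase less in response to the maximum load exercise than during the endpoint exercise assessment".

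The Summary that closes Background and Significance expects that participants will at first miss the "benefits of exercise due to deficits in the release of the antinociceptive molecules ALLO +PA", and that training will progressively increase that release. Under Pilot data, the Additional findings report a correlation of .77 between VO2 max and change in ALLO, and infer that "regular exercise leading to an increase in VO_2 max may result in an increase in the capacity for release". The same section describes the pilot participants as including people both with and without chronic pain and PTSD.

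In the Data Analyses section, the paragraph for Aims 2 & 3 says that at both exercise assessments "change scores will be computed ALLO+PA and these will be correlated with pain tolerance and pain threshold scores". It adds an exploratory regression of pain outcomes on ALLO+PA. PTSD severity appears beside ALLO+PA in two other places: the hypothesis under Exploratory Aim 1, which expects people with larger acute ALLO+PA increases to have lower PTSD severity, and the matching list of correlations in the analysis section.

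**The concern.** The aim asks for a contrast over PTSD severity. The hypothesis supplies a contrast over time in the same people. The analysis paragraph supplies neither, because it relates ALLO+PA change to pain scores. Followed exactly, the plan gives no result that answers Aim 2.

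The gap matters because the protocol itself offers a second explanation for a rise. If ALLO release follows fitness, a 12-week programme that raises VO2 max should raise the response in people with no deficit. A positive Hypothesis 2a would be compatible with a corrected PTSD-related deficit and equally with an ordinary training effect. A null result would not exclude a deficit at baseline. Under Specific Objectives, the pilot is to supply effect sizes for a later trial, so an ambiguous rise could be carried forward as a PTSD mechanism.

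**Working it through.** **1. Where severity and ALLO+PA meet.**

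| Place | Contrast | PTSD-severity term? | Test of baseline vs endpoint ALLO+PA? |
|---|---|---|---|
| Aim 2 | Training impact, varying severity | Implied | Implied |
| Hypothesis 2a | Baseline vs own endpoint | No | Stated as a prediction |
| Analysis, Aims 2 & 3 | ALLO+PA change vs pain scores | No | No |
| Analysis, Aim 1 | Two dummy-coded groups, symptom outcomes | Group only | No |
| Exploratory hypothesis and correlation list | Acute ALLO+PA response vs PTSD severity, among others | Yes | No |

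No row tests whether the ALLO+PA training effect differs by severity.

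**2. The plan's own figure.** The Power and Sample Size paragraph gives 25 participants for 90% power at a Cohen's effect size of .35, two-sided 5%. It does not say which index or test. Read as a paired standardized difference, .35 needs 88 participants and gives power .39 at 25. Read as Cohen's f with two time points and an assumed correlation of .5, it needs 24. The figure is therefore neither confirmed nor refuted, and it gives no power for a severity contrast.

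**3. What a general fitness effect alone would produce.** Assume no PTSD-related deficit.
- Inputs: pilot r = .77, used as a training slope in line with the protocol's own inference; n = 25 completers. The VO2 max gain (in SD) and the test-retest correlation ρ of the response are not in the documents and are assumed.
- Shift in response = .77 × gain: .77 × .25 = .19; .77 × .5 = .39; .77 × .75 = .58 SD.
- Standardized paired change dz = shift / √(2(1−ρ)). At ρ = .5 the divisor is 1, so dz equals the shift.
- Probability of a significant two-sided paired t test (noncentral t):

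| VO2 gain (SD) | ρ = .3 | ρ = .5 | ρ = .7 |
|---|---|---|---|
| 0.25 | .12 | .15 | .22 |
| 0.50 | .35 | .46 | .67 |
| 0.75 | .65 | .79 | .95 |

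These are the chances that a genuine but general rise is detected. They are not false-positive rates. The slope is itself uncertain: the pilot regression has F(2,9), which implies 9 + 2 + 1 = 12 participants. If the correlation used the same 12, its 95% interval is tanh(1.020 ± 1.96/√9), or about .35 to .93.

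**4. A check that does not use the pilot slope.** Simulate 25 people with an identical expected rise of dz = 0.7 (assumed), unrelated to PTSD, 20,000 runs. The baseline-versus-endpoint test is significant in 92% of runs. A test of change against severity rejects in 5.0%, its nominal level. Only the second contrast bears on severity.

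**5. What a severity slope can detect.** By Fisher z, detectable r at 80% power = tanh(2.80/√(n−3)). At n = 30 this is tanh(2.80/5.196) = .49; at n = 25, tanh(2.80/4.690) = .54. Power for r = .5 is .81 at n = 30 and .73 at n = 25; for r = .3 it is .36 and .31.

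**6. Why a baseline severity regression must also be shown adjusted for fitness.** Suppose severity and VO2 max correlate at −.3 to −.5 (assumed) and PTSD has no direct effect. The induced correlation of severity with the ALLO+PA response is .77 × −.3 = −.23 to .77 × −.5 = −.39. At n = 30 an unadjusted regression would then reject about 23% to 56% of the time.

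**The case against.** The strongest reply is that the protocol already links severity to the acute ALLO+PA response. The hypothesis under Exploratory Aim 1 gives a direction and names the acute response, and that aim covers the baseline and endpoint assessments. This stands: a reader who inferred that the protocol never relates the two would be wrong. What remains is that the link is exploratory, sits in a long list from which regression predictors are then chosen, and does not test whether the training effect differs by severity.

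A second reply is that Aim 2's wording about severity may only describe the sample, and that the Summary attributes the initial deficit to the whole study population. It also frames the objective as whether exercise affects ALLO+PA. That reading is possible for Aim 2 alone. It sits less well with the instruction to compare and with the problem statement's PTSD-related deficiencies. It also leaves Hypothesis 2a without a planned test.

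Two stronger readings are tempting and are not supported. One is that the sponsor has committed to reporting any rise as a corrected PTSD-related deficit. Neither Hypothesis 2a nor the analysis section says so; it is an inference from the problem statement and the Summary. The other is that .15, .46 and .79 show an inflated Type I error against .05. Under those assumptions the response truly rises, so that part of Hypothesis 2a is true; what fails is the step from the rise to a PTSD-related cause.

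The two dummy-coded groups do not close the gap. They are specified only for the Aim 1 symptom models, and no group sizes are given.

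**Conclusion.** The point holds as a mismatch between aim and analysis. Aim 2's severity comparison has no designated result, Hypothesis 2a has no stated test, and a baseline-to-endpoint rise alone cannot support a PTSD-related deficit or its correction. This follows from the text and does not depend on the numbers.

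The numbers illustrate how readily a general effect could appear: from .12 to .95 across assumed VO2 gains of 0.25 to 0.75 SD and test-retest correlations of .3 to .7. They rest on a small cross-sectional pilot correlation used as a within-person slope. The matter is worth correcting because the correction costs almost nothing, although this is pilot work and the severity slopes will be estimated imprecisely.

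**What to change.** Amend the Aims 2 & 3 paragraph of the analysis section.

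1. For Aim 2, regress the endpoint ALLO+PA response (pre-exercise to 30 minutes after exercise) on the pre-training continuous CAPS-5 severity score, adjusted for the baseline response. Report the baseline-to-endpoint change itself alongside. Where the CAPS-5 was repeated because a month or more had passed since screening, state which score is used.
2. Move the association between the baseline ALLO+PA response and CAPS-5 severity from the exploratory aim into Aim 2 as a prespecified regression. Report it with and without adjustment for baseline peak VO2. Both are needed: the unadjusted slope can reflect fitness, and the adjusted one may remove part of a PTSD effect that acts through fitness. Note chronic pain status if participants without pain are enrolled, as the inclusion criteria appear to allow.
3. Report both severity slopes as estimates with confidence intervals. State in Aim 2 that a baseline-to-endpoint rise alone shows change over the programme and will not be reported as evidence, or correction, of a PTSD-related deficit.

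The cost is wording and two regressions. CAPS-5, peak VO2 and the blood samples are already scheduled, so no visits, assays or participants are added. The downside is that correlations below about .5 are likely to be missed and the conclusion from Hypothesis 2a becomes more modest.
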